7.1 Demographic and Baseline Characteristics

Demographics include age, weight, height and BMI as continuous variables, and sex, race, ethnicity, age category (< 55 years or ≥ 55 years] and [< 65 or ≥ 65 years]), birth year (< 1945 , 1945 to 1965, > 1965), country, and BMI category (< 30 kg/m² or ≥ 30 kg/m²).

Baseline characteristics will include: HCV genotype 1 subtype (1a, 1b, 1-other), IL28B genotype ([CC, CT, or TT] and [CC or non CC]), prior treatment history (treatment-naïve [IFN-eligible, IFN-ineligible] or IFN-based treatment-experienced [null responder, partial responder, relapser, prior relapse/breakthrough, prior nonresponder, IFN-intolerant and IFN experienced-other]), baseline HCV RNA levels ([continuous (use log₁₀ HCV RNA)])

and [$< 800,000$ IU/mL or $\geq 800,000$ IU/mL]), baseline HOMA-IR (< 3 or ≥ 3 $\text{mU} \times \text{mmol/L}^2$), baseline fibrosis stage (F0 – F1, F2, F3, F4), baseline Child-Pugh score (non-cirrhotic, 5, 6, or > 6), baseline FibroTest score (continuous and [< 0.49 , $0.49 - 0.58$, $0.59 - 0.74$, ≥ 0.75]), baseline albumin (continuous), baseline albumin (< 35 , ≥ 35 g/L), baseline creatinine clearance (continuous; < 30 mL/min, $\geq 30 - 49$ mL/min, $\geq 50 - 89$ mL/min, ≥ 90 mL/min), baseline eGFR by MDRD (continuous; < 30 , $30 - 59$, $60 - 89$, ≥ 90 mL/min/1.73 m²; < 60 or ≥ 60 mL/min/1.73 m²), baseline platelet count (continuous; $< 90 \times 10^9/\text{L}$, $\geq 90 \times 10^9/\text{L}$; $< 50 \times 10^9/\text{L}$, $\geq 50 \times 10^9/\text{L}$; $< 100 \times 10^9/\text{L}$, $\geq 100 \times 10^9/\text{L}$; $< 150 \times 10^9/\text{L}$, $\geq 150 \times 10^9/\text{L}$), baseline alpha fetoprotein (continuous, and < 20 ng/mL, ≥ 20 ng/mL), tobacco (user, ex-user, or non-user) and alcohol (drinker, ex-drinker, or non-drinker) use status, history of diabetes, history of depression or bipolar disorder, history of bleeding disorders, AST to platelet ratio index (APRI) (continuous; ≤ 2.0 or > 2.0), and Fibrosis-4 score (FIB-4) (continuous; ≤ 3.25 , > 3.25).

Subjects' HCV genotype and subtype may be assessed based on the Inno-LiPA 2.0 Assay used by the Central lab, the ARUP Assay for Hepatitis C High-Resolution Genotype by the Central lab and/or from phylogenetic analysis of the full length NS3/4A, NS5A, and/or NS5B sequences performed by AbbVie. If the phylogenetic analysis is available it will be used to determine the subject's HCV genotype and subtype. If it is not available, then the ARUP assay result will be used to determine the subject's HCV genotype and subtype, if available. Finally, if neither the phylogenetic analysis result nor the ARUP assay results are available, then the Inno-LiPA assay results will be used to categorize the subject.

Subjects' baseline fibrosis stage will be assessed by investigator during the screening period and categorized as F0 – F1, F2, F3, or F4.

For subjects with baseline fibrosis stage of F4, the baseline Child-Pugh score is determined by the Day 1 assessment of ascites and hepatic encephalopathy along with the baseline values of total bilirubin, serum albumin, and international normalized ratio (INR). The Child-Pugh score is the sum of the point assigned for each of the five observed findings as defined in [Table 7](#).

Table 7. Child-Pugh Classification of Severity of Cirrhosis

Parameter	Points Assigned for Observed Findings		
	1	2	3
Total bilirubin, µmol/L (mg/dL)	< 34.2 (< 2)	34.2 – 51.3 (2 – 3)	> 51.3 (> 3)
Serum albumin, g/L (g/dL)	> 35 (> 3.5)	28 – 35 (2.8 – 3.5)	< 28 (< 2.8)
INR	< 1.7	1.7 – 2.3	> 2.3
Ascites*	None	Slight	Moderate to severe
Hepatic encephalopathy**	None	Grade 1 or 2 (or suppressed with medication)	Grade 3 or 4 (or refractory)

* None.

Slight ascites = Ascites detectable only by ultrasound examination.

Moderate ascites = Ascites manifested by moderate symmetrical distension of the abdomen.

Severe ascites = Large or gross ascites with marked abdominal distension.

** Grade 0: normal consciousness, personality, neurological examination, electroencephalogram.

Grade 1: restless, sleep disturbed, irritable/agitated, tremor, impaired handwriting, 5 cps waves.

Grade 2: lethargic, time-disoriented, inappropriate behavior, asterixis, ataxia, slow triphasic waves.

Grade 3: somnolent, stuporous, place-disoriented, hyperactive reflexes, rigidity, slower waves.

Grade 4: unarousable coma, no personality/behavior, decerebrate, slow 2 to 3 cps delta activity.

Baseline APRI and FIB-4 are defined as the equations below. Subjects without baseline values of AST, platelet count or age will be excluded from the summary of APRI; subjects without baseline values of AST, ALT, platelet count, or age will be excluded from the summary of FIB-4.

$$\text{APRI} = \frac{\frac{\text{AST Level (IU/L)}}{\text{AST (Upper Limit of Normal)(IU/L)}}}{\text{Platelet Count (10}^9\text{/L)}} \times 100$$

$$\text{FIB-4} = \frac{\text{Age (years)} \times \text{AST Level (U/L)}}{\text{Platelet Count (10}^9\text{/L)} \times \sqrt{\text{ALT (U/L)}}}$$

Summary statistics (N, mean, median, standard deviation [SD], and range) will be generated for continuous variables (e.g., age and BMI) and the number and percentage of subjects will be presented for categorical variables (e.g., sex and race).

7.2 Medical History

Medical history data will be summarized and presented using body systems and conditions/diagnoses as captured on the eCRF. The body systems will be presented in alphabetical order and the conditions/diagnoses will be presented in alphabetical order within each body system. The number and percentage of subjects with a particular condition/diagnosis will be summarized. Subjects reporting more than one condition/diagnosis within a body system will be counted only once for that body system.

7.3 Previous Treatment and Concomitant Medications

Prior and concomitant medications will be summarized. A prior medication is defined as any medication taken prior to the date of the first dose of study drug. A concomitant medication is defined as any medication that started prior to the date of the first dose of study drug and continued to be taken after the first dose of study drug or any medication that started on or after the date of the first dose of study drug, but not after the date of the last (maximum) dose of study drug. Concomitant medications will be summarized for all subjects in the Safety population. The number and percentage of subjects taking prior or concomitant medications will be summarized by generic drug name based on the WHO Drug Dictionary. Note that prior HCV medications (IFN, pegIFN and RBV) will be summarized separately from other prior medications.

Medications for the treatment of HCV will be collected in the PT Period and will be summarized by generic drug name. A post-treatment medication for the treatment of HCV is defined as any medication taken on or after the last dose of study drug and entered as "Post treatment HCV medications" on the eCRF.

8.0 Patient Disposition

The number of subjects for each of the following categories will be summarized overall and by each investigator on the safety population.

- Subjects who took at least one dose of study drug;
- Subjects who completed study drug;
- Subjects who discontinued from study drug;
- Subjects who completed the study;
- Subjects ongoing in the Post-Treatment Period at the time of the interim analysis;
- Subjects who discontinued from the study.

The number and percentage of subjects who discontinued study drug will be summarized by reason (all reasons) and by primary reason (per eCRF). Similar summaries will be provided for discontinuations from the study.

The number and percentage of subjects will be summarized for:

- Subjects with interruptions of all study drugs for toxicity management;
- Subjects with any RBV dose modification;
 - Subjects with RBV dose modification due to decrease in hemoglobin;
 - Subjects with RBV dose modification due to decrease in creatinine clearance;
 - Subjects with RBV dose modification due to weight change;
 - Subjects with RBV dose modification due to other reasons;
- Subjects with any RBV dose modification to 0 mg (i.e., RBV interruptions).

Reasons for study drug interruptions and RBV dose modifications will be presented in the CSR listings.

9.0 Study Drug Exposure and Compliance

9.1 Exposure

The duration of exposure to study drug will be summarized in the safety population. Duration of exposure is defined for each subject as the last study drug dose date minus the first study drug dose date plus 1 day.

Descriptive statistics (n, mean, SD, median, minimum and maximum) will be presented. Study drug duration also will be summarized with frequencies and percentages using the following categories depending on the treatment duration:

- 12 weeks of treatment: 1 to 15 days, 16 to 30 days, 31 to 45 days, 46 to 60 days, 61 to 76 days, and > 76 days.
- 24 weeks of treatment: 1 to 15 days, 16 to 30 days, 31 to 60 days, 61 to 90 days, 91 to 120 days, 121 to 153 days, and > 153 days.

9.2 Compliance

At each protocol-specified visit, the total number of tablets dispensed and returned is recorded together for ABT-450/r/ABT-267 and ABT-333, and is recorded separately for RBV. The compliance for ABT-450/r/ABT-267 and ABT-333 combined and the compliance for RBV within the Treatment Period will be calculated as the percentage of tablets taken relative to the total tablets, respectively, expected to be taken. The total number of tablets prescribed will be equal to the total number of tablets that should have been taken per the protocol for the duration that the subject was in the Treatment Period (date of last dose – date of first dose + 1 day). Study drug interruptions due to an adverse event or other planned interruptions recorded on the eCRF will be subtracted from the duration. For compliance to RBV, RBV dose modifications due to adverse events, toxicity management, or weight changes as recorded on the RBV Dose Modifications eCRF will be used to modify the total number of tablets that should have been taken. A subject is considered to be compliant if the percentage is between 80% and 120%. Compliance will be calculated for each subject and summarized with the N, mean, SD,

median, minimum and maximum. In addition, the percentage of compliant subjects will be calculated separately for ABT-450/r/ABT-267 + ABT-333, and RBV.

10.0 Efficacy Analysis

10.1 General Considerations

The primary efficacy analysis on clinical outcomes will be performed on all subjects in the ITT population as defined in Section 5.1. All other efficacy analyses will be performed on the ITT-I population.

Treatment effects will be evaluated based on a two-sided significance level of 0.05 (when rounded to three decimal places). The data from the ITT-I population will be presented in one column/row as it represents the labelled treatment.

Plasma HCV RNA levels will be determined for each sample collected by the central laboratory using the COBAS[®] AmpliPrep/COBAS[®] TaqMan[®] HCV Test, v2.0. For this assay, the lower limit of quantification (LLOQ) and the lower limit of detection (LLOD) is 15 IU/mL. HCV RNA results that are detectable but not quantifiable are reported as "< 15 IU/mL" and results that are not detectable are reported as "NON-DETECTED."

Assessment of Clinical Outcomes

Incidence of the following clinical outcome events will be collected during the 12/24 weeks of treatment and the 5-year (PT Week 260) Post-Treatment Period. Data will be adjudicated by an independent outcome committee and results will be reported in the "Clinical Outcome" eCRFs:

- All-cause death: Death due to any cause.
- Liver-related death: Death as the result of a liver-related cause.
- Liver decompensation: Development of any of the following conditions: ascites, hepatic encephalopathy, or variceal bleeding.
- Liver transplantation: any subject who had a liver transplantation.

- Hepatocellular carcinoma (HCC): development of HCC in any subject at any time during the study. HCC is defined by histologic confirmation or a > 1 cm mass lesion on cross-sectional imaging that meets the diagnostic criteria for HCC according to EASL guidelines.
- Composite of any of the above outcomes.

Definitions for HCV RNA Efficacy Endpoints

Note that a confirmed quantifiable post-treatment value is defined as two consecutive post-treatment HCV RNA measurements \geq LLOQ. During treatment, a confirmed quantifiable value is defined as any two consecutive HCV RNA values \geq LLOQ, either both during treatment or at the final treatment measurement and the next consecutive post-treatment measurement.

Breakthrough = confirmed HCV RNA \geq LLOQ after HCV RNA < LLOQ during treatment, or confirmed increase from nadir in HCV RNA (two consecutive HCV RNA measurements > 1 log₁₀ IU/mL above nadir) at any time point during treatment. A single breakthrough value (\geq LLOQ or > 1 log₁₀ IU/mL above nadir) followed by lost to follow-up will be considered a breakthrough (i.e., will not require confirmation).

On-treatment virologic failure = breakthrough or failure to suppress during treatment (all on-treatment values of HCV RNA \geq LLOQ) with at least 6 weeks (defined as study drug duration \geq 36 days) of treatment.

RVR (rapid virologic response) = HCV RNA < LLOQ in the Week 4 window.

EOTR (end of treatment response) = HCV RNA < LLOQ in the Week 12 window for subjects receiving 12 weeks of treatment and in the Week 24 window for subjects receiving 24 weeks of treatment.

SVR₄ = HCV RNA < LLOQ in the SVR₄ window (4 weeks after the last actual dose of study drug) without any confirmed quantifiable (\geq LLOQ) post-treatment value during that SVR window.

SVR₁₂ = HCV RNA < LLOQ in the SVR₁₂ window (12 weeks after the last actual dose of study drug) without any confirmed quantifiable (\geq LLOQ) post-treatment value before or during that SVR window.

SVR₂₄ = HCV RNA < LLOQ in the SVR₂₄ window (24 weeks after the last actual dose of study drug) without any confirmed quantifiable (\geq LLOQ) post-treatment value before or during that SVR window.

Relapse₁₂ = confirmed HCV RNA \geq LLOQ between end of treatment and 12 weeks after last actual dose of active study drug (up to and including the SVR₁₂ assessment time point) for a subject with HCV RNA < LLOQ at Final Treatment Visit who completes treatment.

Relapse₂₄ = confirmed HCV RNA \geq LLOQ during SVR₂₄ window among subjects who achieved SVR₁₂ and have data available during the SVR₂₄ window.

Relapse_{late} = confirmed HCV RNA \geq LLOQ at any time after the SVR₂₄ assessment time point for a subject who achieved SVR₂₄ and has post-SVR₂₄ HCV RNA data available.

Relapse_{overall} = confirmed HCV RNA \geq LLOQ between end of treatment and up to and including the last HCV RNA measurement collected in the PT Period for a subject with HCV RNA < LLOQ at Final Treatment Visit who completes treatment. For relapse analyses, the completion of treatment is defined as a study drug duration \geq 77 days for subjects assigned to 12 weeks of treatment and \geq 154 days for subjects assigned to 24 weeks of treatment. If the last available post treatment value is \geq LLOQ, then the subject will be considered a relapse (i.e., will not require confirmation). Relapse analyses will exclude subjects who do not have any post-treatment HCV RNA values.

HCV re-infection is defined as confirmed HCV RNA \geq LLOQ after the end of treatment in a subject who had HCV RNA < LLOQ at Final Treatment Visit, along with the post-treatment detection of a different HCV genotype, subtype, or clade compared with baseline, as determined by phylogenetic analysis of the NS3 or NS5A, and/or NS5B gene sequences. Re-infection in the case of the same HCV subtype is defined as a clade

switch, as indicated by the lack of clustering between the baseline and post-treatment sequences by phylogenetic analysis. If phylogenetic analysis is not possible due to technical difficulties, HCV re-infection may be determined with a confirmed HCV genotype or subgenotype switch by the Versant HCV Genotype Inno-LiPA Assay v2.0 or Sanger assay.

Any subjects with documented re-infection will be excluded from relapse analyses and will be analyzed separately.

Reasons for SVR₁₂ Non-Response

Subjects who do not achieve SVR₁₂ (SVR₁₂ non-responders) will be categorized as having:

1. On-treatment virologic failure (see **On-treatment virologic failure** definition);
2. Relapse (defined according to the **Relapse₁₂** definition for subjects who complete treatment);
3. Prematurely discontinued study drug with no on-treatment virologic failure (defined as any SVR₁₂ non-responder who prematurely discontinued study drug (duration < 77 days for subjects assigned to 12 weeks of treatment or duration < 154 days for subjects assigned to 24 weeks of treatment) and did not meet the **On-treatment virologic failure** definition);
4. Missing follow-up data in the SVR₁₂ window [defined as any subject who completed study drug without data in the SVR₁₂ window and not meeting the definitions of (1), (2), or (3)];
5. Other (including subjects with documented re-infections and subjects defined as any SVR₁₂ non-responder not meeting the definitions of [1] – [4], such as a subject with a single quantifiable value within the SVR₁₂ window followed by an undetectable value beyond the SVR₁₂ window).

Reasons for SVR₂₄ Non-Response

Subjects who do not achieve SVR₂₄ (SVR₂₄ non-responders) will be categorized as having:

1. On-treatment virologic failure (see **On-treatment virologic failure definition**);
2. Relapse (defined according to the **Relapse₁₂** definition for subjects who complete treatment);
3. Relapsed after achieving SVR₁₂ (see **Relapse₂₄**);
4. Prematurely discontinued study drug with no on-treatment virologic failure (defined as any SVR₂₄ non-responder who prematurely discontinued study drug and did not meet the **On-treatment virologic failure**, **Relapse₁₂**, or **Relapse₂₄** definitions);
5. Missing follow-up data in the SVR₂₄ window [defined as any subject who completed study drug without data in the SVR₂₄ window, and not meeting the definitions of (1), (2), (3), or (4)];
6. Other (including subjects with documented re-infections and subjects defined as any SVR₂₄ non-responder not meeting the definitions of [1] – [5]).

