#### **5.4.3 Discontinuation of Subjects that Meet Virologic Failure Criteria**

The following criteria will be considered evidence of virologic failure:

- Confirmed increase from nadir in HCV RNA (defined as 2 consecutive HCV RNA measurements of  $> 1 \log_{10}$  IU/mL above nadir) at any time point during treatment;
- Confirmed HCV RNA  $\geq$  LLOQ (defined as 2 consecutive HCV RNA measurements  $\geq$  LLOQ) at any point after HCV RNA  $<$  LLOQ

Confirmatory testing for the above criteria should be completed as soon as possible. Subjects receiving study drug treatment should remain on treatment until the virologic failure has been confirmed.

If any of the above criteria are confirmed for subjects during study drug treatment, the subject will discontinue treatment. If the investigator believes the virologic failure is due to study drug interruption and/or is compliance related, the AbbVie Study Designated Physician should be contacted to discuss alternative management.

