6.1.4 Final Treatment Value

The final treatment value for each subject is the last non-missing measurement collected after Study Day 1 and on or before Study Drug End Day 2.

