6.2 Analysis Windows

For efficacy analyses of HCV RNA and resistance, the time windows specified in [Table 2](#) and [Table 3](#) describe how efficacy data are assigned to protocol-specified time points during the Treatment and PT Periods, respectively. All time points and corresponding time windows are defined based on the blood sample collection date.

For analyses of health-related quality of life (QoL) PROs collected throughout the study, the time windows specified in [Table 4](#) will be used.

For laboratory data and vital signs, the time windows specified in [Table 5](#) and [Table 6](#) describe how data are assigned to protocol specified time points during the Treatment and PT Periods, respectively.

If more than one assessment is included in a time window, the assessment closest to the nominal time will be used. If there are two observations equally distant to the nominal time, the latest one will be used in analyses. The only exception to this is for the SVR windows (e.g., SVR₄, SVR₁₂, and SVR₂₄); for these windows, the last value in the window will be used.

If multiple measurements are made on the same day for a safety laboratory parameter or a vital sign parameter, the average of the values will be used in analyses. For summaries of shifts from baseline and potentially significant values, multiple values on the same day will not be averaged; all values will be considered for these analyses.

Table 2. Analysis Time Windows for HCV RNA and Resistance Endpoints (Treatment Period)

Scheduled Visit	Nominal Day (Study Day)	Time Window (Study Day Range)
Day 1/Baseline ^a	1a	≤ 1 ^a
Week 2	14	2 to 21
Week 4	28	22 to 56
Week 12	84	57 to 126
Week 24 ^b	168	127 to 182
Final Treatment Visit ^c		2 to ≤ 2 days after last dose of study drug

a. Day of first dose of study drug.

b. Week 24 Visit is only applicable to subjects assigned to 24 weeks of treatment.

c. The last value within the window will be used to define the Final Treatment visit value.

Note: Data must also have Study Drug End Day ≤ 2 for all windows. The result closest to the scheduled time point will be used.

Table 3. Analysis Time Windows for HCV RNA and Resistance Endpoints (Post-Treatment Period)

Scheduled Visit^a	Nominal Day (Study Drug End Day)	Time Window (Study Drug End Day Range)
Post-Treatment Week 4	28	3 to 56
Post-Treatment Week 12	84	57 to 126
Post-Treatment Week 24	168	127 to 266
Post-Treatment Week 52	364	267 to 546
Post-Treatment Week 104	728	547 to 910

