Post-Treatment Week 156	1092	911 to 1274
Post-Treatment Week 208	1456	1275 to 1638
Post-Treatment Week 260	1820	1639 to 2002
SVR ₄ ^b	28	3 to 56
SVR ₁₂ ^b	84	57 to 126
SVR ₂₄ ^b	168	127 to 210

a. Post-Treatment Visits are applicable for subjects who received at least one dose of study drug.

b. For SVR windows, the last value in the window will be used.

Note: The result closest to the scheduled time point will be used, except for SVR₄, SVR₁₂, and SVR₂₄. Data must also have Study Drug End Day > 2 for all windows. Study Drug End Day 0 is defined as the day of the last dose of study drug.

Table 4. Analysis Time Windows for PRO Instruments

Scheduled Visit^a	Nominal Day (Study Day)	Time Window (Study Days Range)
Day 1/Baseline	1 ^b	≤ 1 ^b
Week 4	28	2 to 56
Week 12	84	57 to 126
Week 24 ^c	168	127 to 182
Final Treatment Visit ^d		2 to ≤ 2 days after last dose of study drug

Scheduled Visit	Nominal Day (Study Drug End Day)	Time Window (Study Drug End Days Range)
Post-Treatment Week 4	28	3 to 56
Post-Treatment Week 12	84	57 to 126
Post-Treatment Week 24	168	127 to 266
Post-Treatment Week 52	364	267 to 546
Post-Treatment Week 104	728	547 to 910
Post-Treatment Week 156	1092	911 to 1274
Post-Treatment Week 208	1456	1275 to 1638
Post-Treatment Week 260	1820	1639 to 2002
Final Post-Treatment Visit ^e		> 2 days after last dose of study drug

a. SF-36v2 and FACIT-F are collected at Baseline, Week 4, Week 12 and Week 24 (for subjects with 24 weeks of treatment), and Post-Treatment Weeks 4, 12, 24, 52, 104, 156, 208 and 260.

b. Day of first dose of study drug.

c. Applicable to subjects with 24 weeks of treatment.

d. The last value within the window will be used to define the Final Treatment visit value. The upper bound of this Final window is Study Drug End Day ≤ 2.

e. The last value within the Post-Treatment Period window will be used to define the Final Post-Treatment visit value. The lower bound of this Final window is Study Drug End Day 3.

Note: The result closest to the scheduled time point will be used. For visits through Treatment Week 24, data must also be within 2 days after the last dose of study drug. For post-treatment visits, data must also have Study Drug End Day > 2 where Study Drug End Day 0 is defined as the day of the last dose of study drug.

Table 5. Laboratory Data and Vital Sign Visit Windows (Treatment Period)

Scheduled Time	Nominal Day (Study Day)	Time Window (Study Days Range)
Day 1/Baseline ^a	1	≤ 1
Week 2	14	2 to 21
Week 4	28	22 to 56

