10.7 Additional Efficacy Analyses

The following additional HCV RNA efficacy endpoints will be summarized and analyzed on the ITT-I population, as specified:

- The number and percentage of subjects with on-treatment virologic failure;
- The number and percentage of subjects with post-treatment relapse;
- The number and percentage of subjects with documented re-infection;
- The number and percentage of subjects with RVR;
- The number and percentage of subject with EOTR;
- The number and percentage with unquantifiable HCV RNA at each post-baseline visit throughout the Treatment Period (using data from the central laboratory as observed, i.e., no imputation for missing data);
- The number and percentage of subjects with HCV RNA < LLOQ 24 weeks after the last actual dose of study drug (SVR₂₄);
- Reasons for not achieving SVR₂₄ for subjects who do not;
- Mean change from baseline in prothrombin time (PT), International normalized ratio (INR), FibroTest, and albumin to each applicable post-baseline time point;
- The number of subjects who fail to suppress and accompanying listing;
- The number of subjects who breakthrough any time during treatment and accompanying listing;
- The number of completers with final on-treatment HCV RNA < LLOQ who relapse within the SVR₄ window, SVR₁₂ window, or SVR₂₄ window and accompanying listing;
- The concordance between SVR₁₂ and SVR₂₄ will be assessed.

In the above analyses that use the number and percentage of responders, 2-sided 95% Wilson score confidence interval for a binomial proportion will be calculated.

Imputations for missing data will be performed as described in Section 6.3 for analyses of SVR, RVR, and EOTR, where a missing response will be imputed as a failure after performing the described imputation. All other endpoints will be presented using data as observed. For the change from baseline to each post-baseline time point in PT/INR, Fibrotest, and albumin, descriptive statistics will be calculated.

The number and percent of subjects who fail to suppress HCV RNA and received at least 6 weeks of treatment (active study drug duration ≥ 36 days) will be tabulated along with the subject numbers corresponding to the subjects who failed to suppress.

The number of subjects who breakthrough at any time during treatment and within each protocol-specified visit (defined in Table 2) will be summarized along with a corresponding listing displaying the subject numbers at the first occurrence of breakthrough.

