10.8 Resistance Analyses

If possible, subjects treated with study drug who experience virologic failure will have resistance testing conducted if 1) they have on-treatment breakthrough; 2) if they have post-treatment relapse, with a study drug duration ≥ 77 days for subjects assigned to 12 weeks of treatment or with a study drug duration ≥ 154 days for subjects assigned to 24 weeks of treatment; or 3) if they have at least 6 weeks of treatment and fail to suppress by Week 6 (i.e., meet virologic stopping criteria). Subjects meeting one of these criteria will be referred to as subjects in the primary virologic failure (PVF) population, and a listing by subject that includes HCV subtype, IL28B genotype, reason for non-response, time point(s) sequenced as closest to time of VF, and HCV RNA value at the VF time point(s) will be produced for these subjects. In addition, all listings described below will display HCV subtype and reason for non-response in the subject identifier for each subject. A separate listing will delineate all subjects in the PVF population for whom no sequencing was performed (e.g., lost to follow-up while HCV RNA ≤ 1000 IU/mL).

Only samples with an HCV RNA level of ≥ 1000 IU/mL will undergo sequence analysis in order to allow accurate assessment of products of amplification. Therefore if the HCV RNA level at the time of virologic failure (VF) is < 1000 IU/mL, the sample closest in time after the failure with an HCV RNA level ≥ 1000 IU/mL will be used if available.

The regions of interest for next generation sequencing (NGS) from all evaluated time points in this study are those encoding full length NS3/4A, NS5A, and NS5B. The prototypic reference sequences used for analysis will be H77 for genotype 1a or Con1 for genotype 1b.

For each DAA target, resistance-associated amino acid variants will be identified by AbbVie Clinical Virology. Amino acid positions where resistance associated variants have been identified in vitro and/or in vivo are 1) for ABT-450: 36, 43, 55, 56, 80, 155,

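### Failure to suppress (SAP 10.1) requires 36 days of drug but no HCV RNA sample from Day 36 on, so a suppressed subject, even an SVR12 responder, can be counted as an on-treatment virologic failure

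*SAP*

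**What the plan says.** SAP 10.1 defines the endpoint as "On-treatment virologic failure = breakthrough or failure to suppress during treatment (all on-treatment values of HCV RNA" at or above the LLOQ). The exposure condition attached to it is "with at least 6 weeks (defined as study drug duration" of 36 days or more). No condition is placed on the date of any sample.

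What counts as on-treatment comes from elsewhere in the SAP. Section 6.1.4 takes the final treatment value as "the last non-missing measurement collected after Study Day 1 and on or before Study Drug End Day 2". The note to Table 2 (section 6.2) says "Data must also have Study Drug End Day ≤ 2 for all windows", and the note to Table 3 says of the post-treatment windows "Data must also have Study Drug End Day > 2 for all windows".

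SAP Table 2 has on-treatment HCV RNA visits at Weeks 2, 4, 12 and, for 24-week subjects, 24. Under footnote b of Protocol Table 7, the EOT visit replaces the Week 12 visit for 12-week subjects, while 24-week subjects keep Week 12 as an interim visit.

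SAP 10.7 tabulates "The number and percentage of subjects with on-treatment virologic failure" in the whole ITT-I population, as observed. SAP 10.8 selects subjects for resistance testing by a different phrase: "if they have at least 6 weeks of treatment and fail to suppress by Week 6 (i.e., meet virologic stopping criteria"). Protocol 5.4.3, which opens "The following criteria will be considered evidence of virologic failure", lists two criteria: a confirmed rise from nadir, and a confirmed return to LLOQ or above after a value below it.

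**The concern.** A subject with 36 or more days of drug can be judged on Weeks 2 and 4 alone. If the next sample falls on Study Drug End Day 3 or later, it moves to the post-treatment side and drops out of the failure-to-suppress test, whatever it shows. A one-day difference in the EOT visit can then decide whether a subject is a virologic failure, and the same subject can be reported as both an SVR12 success and an on-treatment failure.

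True on-treatment failures are rare with this regimen, so a few false ones could distort the reported count.

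The phrase in SAP 10.8 adds a second problem. No HCV RNA visit is scheduled at Week 6, and Protocol 5.4.3 contains no failure-to-suppress stopping criterion. Read literally, failing to suppress by Week 6 could also take in a subject quantifiable at Weeks 2 and 4 but suppressed at an on-time Week 12 sample, whom SAP 10.1 excludes.

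**Working it through.** The plan states no figure for this rule, so there is none to reproduce. The check applies the rules to example timelines and then sizes the effect.

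**Rules applied.** Duration = last dose day − first dose day + 1. End Day = sample day − last dose day. A sample is on-treatment if Study Day ≥ 2 and End Day ≤ 2. Failure to suppress = every on-treatment value ≥ 15 IU/mL (the LLOQ) and duration ≥ 36. SVR12 uses the last value in End Days 57 to 126, with no confirmed quantifiable post-treatment value up to then. Relapse12 needs a final treatment value below LLOQ and completed treatment (≥ 77 days for 12-week subjects).

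**Timelines.** All have Day 14 = 900 and Day 28 = 40 IU/mL, with first dose on Day 1. Later samples are undetectable unless stated.

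| Case | On-treatment values | Failure to suppress | SVR12 |
|---|---|---|---|
| 12 weeks, last dose Day 84, EOT Day 86 (End Day 2) | 900, 40, undetectable | No | Yes |
| Same, EOT Day 87 (End Day 3) | 900, 40 | **Yes** | **Yes** |
| Stops Day 40, sample Day 44 (End Day 4); duration 40 ≥ 36 | 900, 40 | **Yes** | **Yes** |
| 24 weeks, Week 12 undetectable, EOT on End Day 5 | 900, 40, undetectable | No | Yes |
| 12 weeks, EOT Day 86, then 50,000 and 200,000 at post-treatment Weeks 4 and 12 | 900, 40, undetectable | No (relapse) | No |
| Same, EOT Day 87 | 900, 40 | **Yes** | No |

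In the last row the final treatment value is the Week 4 value of 40, so Relapse12 cannot apply and a relapse is recorded as on-treatment failure.

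**Other rules that might rescue the subject.** Flanking imputation (SAP 6.3) needs unquantifiable or undetectable values on both sides, and the Week 4 value is quantifiable. Local-laboratory substitution helps only if a local value exists in the right period. SAP 10.7 otherwise uses data as observed. SVR12 depends on post-treatment values only, so it does not exclude on-treatment failure.

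**Which outputs are affected.**
- SVR12 responders: the on-treatment failure and failure-to-suppress counts (10.7), the virologic-failure logistic regression (10.5) and membership of the primary virologic failure (PVF) listing (10.8).
- SVR12 non-responders: also the reason for non-response (10.1). A premature-discontinuation or missing-data case relabelled as on-treatment failure is kept in mITT-I-GT+VF (10.6) when it would otherwise be excluded.

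**Size.** Benchmark from the Phase 3 counts in Protocol section 3.0 (M11-646, M13-098, M13-389, M13-961, the RBV arm of M14-002, and both arms of M13-099):

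(1 + 0 + 0 + 1 + 1 + 1 + 3) / (473 + 296 + 186 + 419 + 100 + 208 + 172) = 7/1854 = 0.38%; 1650 × 7/1854 = 6.2.

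False failures = 1650 × P(quantifiable at Weeks 2 and 4) × P(EOT sample after End Day 2), taking the two as independent. Neither rate is in the documents; the values below are assumptions.

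- 1% and 2%: 1650 × 0.01 × 0.02 = 0.3
- 5% and 5%: 1650 × 0.05 × 0.05 = 4.1
- 10% and 10%: 1650 × 0.10 × 0.10 = 16.5

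These figures run somewhat high, because they apply to all 1650 although most 24-week subjects are protected by the interim Week 12 sample.

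**The case against.** The case for leaving the text alone is that late off-drug samples should be uncommon and that little depends on this endpoint. Protocol 5.4.1 asks for the discontinuation visit no later than 2 days after the last dose (5.1.2 only recommends this). Sites are to supply extra drug when a visit slips (5.1.2), and each weekly card carries a spare day (5.5.2.1). The 10.7 tables are descriptive and come with subject listings, so an SVR12 responder flagged as a failure could be traced. These points lower the likely count but do not remove the fault: the 2-day guidance concerns premature discontinuation, and I found no equivalent limit for a scheduled EOT visit.

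Several stronger readings are tempting, and the documents do not support them:
- *The SVR12 responder distorts the non-response table or mITT-I-GT+VF.* The table covers SVR12 non-responders only, and a genotype 1 SVR12 responder stays in mITT-I-GT+VF whatever the failure flag says.
- *The rule has no confirmation.* Two consecutive quantifiable on-treatment values meet the SAP's own meaning of confirmed. What is missing is a late sample.
- *False resistance data would follow.* Only samples of at least 1000 IU/mL are sequenced. A low-positive subject who then suppresses has none from failure onward and would appear in the listing of PVF subjects without sequencing.
- *The reported rate could more than triple.* That needs both assumed rates at their upper ends together.

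The benchmark is also approximate. The single failure in M13-961 was in the RBV arm of non-cirrhotic GT1b subjects, and GT1b subjects in M11-646 and M13-098 also received RBV. Protocol Table 5 does not give that combination to that group.

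**Conclusion.** The fault is real and confined to secondary outputs. As written, SAP 10.1 can classify a subject as an on-treatment virologic failure on Week 2 and Week 4 values alone, although the next sample is undetectable and SVR12 is achieved. It concerns 12-week subjects, and subjects who stop between Day 36 and Week 12, whose first sample after Week 4 falls on End Day 3 or later. Among non-responders it can relabel a relapse, a premature discontinuation or a missing-data case.

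A reader might infer that the SVR12 rate or the clinical-outcome comparison is at risk. Neither is: SVR12 status does not use this definition.

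The number affected is likely small, and the documents do not allow it to be calculated. About 0 to 16 of 1650 is a range under assumed rates, not an estimate. It matters only because the true count is expected to be about 6. The mismatch between SAP 10.8, the visit schedule and Protocol 5.4.3 stands however often EOT samples are late.

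**What to change.** In SAP 10.1, require for failure to suppress at least one on-treatment HCV RNA value at or above LLOQ at Study Day 36 or later, in addition to the present conditions. State that subjects with no on-treatment sample from Day 36 on are not failures to suppress, and that SVR12 non-responders among them go to the existing premature-discontinuation, missing-data or other categories.

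Using the next post-treatment sample as a fallback is less good: a subject who suppressed unobserved and relapsed early would still be labelled an on-treatment failure, and a subject with no later sample would be left unclassified.

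In SAP 10.8, refer to the 10.1 definition in place of the Week 6 phrase. The SAP and Protocol 5.4.3 must be reconciled on whether such a stopping criterion exists.

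The cost is a few SAP sentences and one derivation flag, using samples already collected and no added visits. The downside is small: a rare true failure without a late on-treatment sample falls into one of the residual categories and so leaves mITT-I-GT+VF. The same applies to a relapse after a late EOT sample, which would go to the other category because Relapse12 still cannot apply. The subject listings should identify such cases.
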